- Apgar scores at 1 and 5 minutes (score 1-10); as reported in medical records.
- Jaundice: as reported in medical records.

- Respiratory distress (including requiring resuscitation): as reported in medical records.
- Feeding method (first feed and feed method at discharge): breastfeeding or artificial feed; as reported in medical records.
- Admission to neonatal special care baby unit (SCBU) or intensive care unit (NICU), high-dependency care, transitional care; as reported in medical records.

In addition, information on any reason for loss to follow up (e.g. late miscarriage, stillbirth, or participant moving to another area) will be sought from medical records in order to account for missing outcome data.

g. Analysis

The aim of the analysis is to explore if any single adiposity measure taken in this study performs better than BMI in terms of predicting women at high-risk of an adverse pregnancy outcome. Each adiposity measure will be assessed individually. If no one measure performs better than BMI, multiple logistic regression models will be used for the analysis of each outcome separately. There won't be any variable selection since our predictors are already fixed. Wherever possible, we will retain continuous candidate predictors in their continuous form to avoid statistical power loss (29). Nonlinear trend in continuous predictors will be explored using either fractional polynomials or restricted cubic splines.

The apparent performance of the developed model will be summarised using calibration, discrimination and internal validation analyses (30). Calibration determines performance in terms of the agreement between the probability of developing the outcome as estimated by the measure/model, and the observed outcome frequencies. Discrimination is the measure of the model's ability to distinguish between individuals who develop the outcome or not (i.e., a higher probability assigned to the individual who develops the outcome compared with an individual who does not. This will be assessed using the c-index (equivalent to the area under the receiver operating characteristic [AUROC] curve).

Any missing values will be assumed to be missing at random (MAR) and multiple imputation (MI) will be implemented using 20 imputations (31). Calibration and discrimination of the developed model(s) will be summarised in the datasets

(averaged over imputation datasets). Calibration will also be assessed graphically (32).

The model will be internally validated using bootstrap re-sampling method in order to quantify the degree of optimism due to overfitting (33, 34) and to derive optimism-adjusted indices of discrimination (c index) and calibration (calibration slope) (35). Two hundred bootstrap samples will be used (36). Optimism is expected when measures/models are applied to the same dataset used for development, as they have been developed to achieve the best fit for that specific dataset (i.e., overfitting). Statistical techniques (e.g., bootstrapping) can quantify the potential for overfitting, and provide adjustment estimates (e.g., shrinkage factor) to reflect the prognostic performance in a new dataset/population.

9. Data storage and management

Data handling, record keeping and access to data

Participant identifiable information will be handled in line with GDPR 2018 principles. Initial data collection and storage will be via Redcap and data will be stored on the NUTH secure server under Caldicott approval until recruitment is complete. At the end of the recruitment period data will be anonymised. All participants will be given a unique identifier to facilitate this. Following completion of all follow up data collection (i.e. from routine maternity records), anonymised electronic research data will be transferred to a Newcastle University secure server for analysis. No personal identifying information will be presented in the study outputs.

The clinical research team and local R&D monitors may require access to the participants' clinical notes; participants will be informed of this in the participant information sheet, and permission to do so will be obtained as part of the consent process.

Archiving

For women who have consented to the SHAPES study, data will be stored securely with restricted access for a period of 5 years after the end of the study. Any

identifiable data will be stored by NUTH, and anonymised research data stored by Newcastle University on a secure server.

Future research: long-term follow-up

Additional consent will also be sought from participants to store their data for future long-term follow up studies. These future studies will explore the association between early pregnancy adiposity and future health-related risks (e.g. for metabolic abnormalities) in women and their offspring. To facilitate linkage of participants' data to other relevant routine datasets in the future (e.g. NHS Digital data), a file containing the 'key' to enable anonymised data to be linked to personal identifiers (i.e. maternal name, date of birth and NHS number, and baby's date of birth and NHS number) will be stored in a separate folder on a Newcastle University secure server, for the participants who consent to this. Access to the separate folder will be restricted to the study's Chief Investigator. Ethical approval will be sought for any future research using this data.

Data Controller

NUTH will be the data controller for the identifiable data collected for the SHAPES Cohort study. For SHAPES participants who consent to the long-term follow up study, Newcastle University will be the data controller (appendix 3).

10. Patient, Public, and Stakeholder Involvement

Pregnant and postnatal women (from here on referred to as mums), clinical stakeholders (obstetricians, midwives, sonographers) and the Research Design Service North East (RDS NE) consumer panel were involved in the development of the proposed research funding application, protocol, and in planning future PPI activities as part of this research.

PPI for research design to date:

Five PPI consultations have been carried out with mums attending a community group (<http://birthbabyandfamily.com>) led by [name], a parent support

specialist. Discussions included: acceptability and timing of adiposity measurements; reviewing the plain English and PPI sections of the funding application; discussing how to communicate research to pregnant women and wider public; future PPI involvement in the research; the process of recruitment involving sending letters and follow up phone calls; the provision of thank you gifts to research participants; reviewing the PIS; and reviewing the recruitment letters to be sent in advance of making their 12-week scan appointment.

PPI members strongly thought this research was a priority. In addition to reviewing and changing the wording on documentation (PIS and recruitment letters), a summary of the additional issues raised and how we have addressed these (in italic) is provided below:

- Mums' felt the planned research was acceptable as they were used to having multiple measurements in pregnancy, although they thought that some women might be uncomfortable with certain adiposity measurements.
 - *We have specified in the PIS that the researcher taking measurements will be female.*
- Suggested strategies to increase recruitment included:
 - Informing women about the research before their scan appointment
 - *We have included information about SHAPES in a routine NUTH research letter which will be sent in advance of the scan appointment.*
 - Phoning women as part of the strategy (linked with previous suggestion) was discussed; women felt this would be acceptable as long as measures were put in place to avoid phoning women who had a miscarriage following the booking appointment
 - *We have included these steps in the recruitment process, including checking patient records for any reported miscarriage, or any warning signs of a threatened miscarriage such as bleeding or attendance at the Early Pregnancy Assessment Clinic (EPAC) or A&E relating to their pregnancy. We will screen the reports of any EPAC/A&E visits to check for adverse outcomes and will only follow up with women who have confirmation of no adverse outcomes or*

suspected adverse outcomes following assessment at the EPAC/A&E.

- Providing clear information on what the measurements involved, and that those measurements were one-off with no follow-up required.
 - *We have included this information in the PIS.*
- Partners/family members tend to be present at scans so privacy while having the extra measurements taken may be an issue.
 - *We have agreement from the clinical team to have a private room available for these measurements. The measurements will also be taken by a female researcher and this is described on the PIS.*
- Options for thank you gifts were discussed. We have the budget to give all women a £5 gift voucher, or photographs of the baby at the 12-week scan appointment plus entry to a prize drawer to win gift vouchers. The provision of photographs was considered an appropriate thank you gift as women would usually have to pay for these, and would be preferable and more meaningful than a £5 gift voucher. The value of a prize draw was also discussed, with women preferring multiple smaller value prizes (e.g. £100) than one or two large value prizes (e.g. £1000).
 - *We have included thank you gifts of mounted photographs from the 12-week scan appointment for all participants, and women can opt into the prize draw if they want to. There are 40 prizes of £100 vouchers in the draw.*

PPI model for the research:

Mums' discussed involvement on steering groups (i.e. PPI collaboration) versus having PPI consultation sessions for the research going forward. They discussed the challenge to PPI collaboration due to the transience of pregnancy versus the lengthy research process. For this reason, PPI consultations were preferable, and we have planned to use this approach throughout the research. However, mums also felt that collaboration would be possible if different PPI representatives could be involved throughout the research rather than having to commit to all of them, as continuity of mums sitting on a steering group was unlikely. It was suggested that non-health

professionals who work with mums (e.g. parent support specialists, breastfeeding peer supporters) could be involved on the steering group for continuity.

- *The PPI plan for this research is based on these discussions with mums. We have planned a series of consultations with mums/parents throughout the research. [name], a non-health professional parent support specialist, will sit on the steering group, and two mums will be invited to each steering group meeting (likely to be different women each meeting, to be supported by [name]).*

PPI training and development support:

We will carry out a PPI training and support needs assessment for PPI representatives attending steering group meetings. They will have access to Newcastle University PPI workshops, Peer to Peer online forum and annual meetings; buddies from the RDS NE consumer panel; online training (<https://www.epaonline.org/>); INVOLVE Public Information Pack and other guidance. Role descriptions will be developed with PPI members using INVOLVE recommendations (e.g. mentoring, continued involvement after the project). We will discuss the topics of steering group meetings at PPI consultation sessions in advance of the meetings so PPI perspectives can be represented by PPI members in attendance at the meetings. Steering group meeting preparation will include pre-meetings with PPI representatives; post-meeting debriefs; a glossary of terms relevant to the research; the steering group will be asked not to use jargon/acronyms; and regular PPI updates between steering group meetings. Mums' felt additional training wasn't required for consultation sessions, and that it was the researcher's responsibility to ensure these were delivered at the right level.

PPI contributions to the dissemination plan:

When discussing communication of research to pregnant women and the wider public, mums' stated their information sources were primarily non-NHS (e.g. pregnancy groups, social-media, bloggers), which has informed the dissemination strategy. Plain English writing will be required for patient and public dissemination. When reviewing the plain English summary of the proposed research for the funding

application, the RDS consumer panel and mums provided some similar and also some different feedback. The RDS consumer panel (not necessarily having recent experience with pregnancy) highlighted additional pregnancy-specific terminology that needed explaining, suggesting that mums are more familiar with pregnancy jargon. Therefore, other generalist PPI groups such as the RDS consumer panel will be consulted when developing written communication to ensure the messages are clear to the wider public.

Stakeholder involvement:

Clinical stakeholders were also involved in the development of the research. Key discussion points included considering the effect of existing guideline interventions for women with a BMI \geq 30kg/m² that women will continue to receive as part of routine care during the research time period; recruitment and measurement logistics in the routine antenatal scan clinics; equipment and training required for midwife sonographers to carry out the additional ultrasound measurements; and processes for recruitment relating to sending out letters and follow up phone calls. Clinical stakeholders will continue to be involved in the Project Management Group and Study Steering Group. Additional stakeholders including policy, practice and third sector organisations (e.g. NICE, Royal College of Midwives, Tommy's the Baby Charity, Association for the Study of Obesity, Royal College of Obstetricians and Gynaecologists) will also be invited onto the Study Steering Group.

11. Dissemination

The SHAPES study is part of an NIHR Advanced Fellowship research programme. The findings of this study, in terms of the variables with the best predictive power, will be validated in a subsequent study using individual participant data meta-analysis methods. An economic evaluation of implementing the alternative approach to risk prediction will also be conducted. All research will be published in peer reviewed journals.

Dissemination of the whole programme of work will focus on maximising its impact on the delivery of routine NHS care. Outputs will be target audience appropriate, for example utilising research briefs, policy briefs, media coverage and stakeholder and

participant communication to achieve this goal. The target audience for this work includes:

- health professionals/organisations (e.g. Royal College of Obstetricians and Gynaecologists, Royal College of Midwives)
- pregnant women and their families
- maternity managers and commissioners of services
- national and international policy makers and decision makers (e.g. NICE, CMO's, WHO)
- wider public and media
- third sector (e.g. Tommy's the Baby Charity, Association for the Study of Obesity)
- academics

12. Ethical considerations

This is a low risk, observational study. Caldicott, Research Ethics Committee and Health Research Authority Approval and will be in place before the study begins. The study sponsor is Newcastle upon Tyne Hospitals NHS Foundation Trust.

The main ethical issue for this study is that women will be asked to spend longer in the antenatal clinic (approximately an additional 45 minutes) when they attend for their routine 12-week scan. This is to allow study specific measurements and data collection to be completed. Participants will not be contacted again after this appointment as outcome data will be obtained from routine records, with participants' consent.

There is the potential for distress to be caused to women if we contact them to see if they would like to take part in the research and they have suffered a miscarriage between the time of their booking appointment and the time they are contacted by the clinical research team. To minimise this risk, the clinical teams will check electronic records for any indication that a miscarriage has occurred, or any warning signs that a miscarriage is likely. This will include any record of miscarriage, as well as checking for any attendance at the EPAC or A&E relating to their pregnancy. To be inclusive, if the reports of these clinical assessments are positive and there are no

potentially adverse outcomes reported, then we will contact these women. In cases where either a miscarriage or early warning signs of a miscarriage have been recorded, women will not be contacted about the study.

Only clinically qualified members of the research team will have access to patient records prior to obtaining informed consent to participate in the study.

13. Efforts to reduce bias

[figure not shown]
We will use standardised approaches to measurement of the adiposity exposure variables. All members of the research team taking the anthropometry measurements will be trained to the international gold standard for these measurements (ISAK). Ultrasound scan measurements will be taken by experienced pregnancy sonographers with training on the non-routine visceral and subcutaneous fat measurements delivered by RV.

14. References

2. NMPA Project Team. National Maternity and Perinatal Audit: Clinical Report 2017. London: RCOG 2017.

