A sample of 1400 women will be recruited to the study. The sample size was based (at the time of grant application and original protocol development) on the 'rule of thumb' that 10 events (cases of the outcome) were required for each variable included in a multi-variable model to predict an outcome (20, 21). However, recent developments in prognostic model research have allowed us to confirm the above sample is sufficient for this study (22). The sample size calculation is based on a maximum of 7 variables being included in the model based on previously published validated prognostic models in pregnancy including between 1 and 7 predictor variables (23, 24, 25) and the least common pregnancy outcome, which is preeclampsia (estimated prevalence of approximately 5-6% of pregnancies in the UK) (26). Targeting a shrinkage factor of $\leq 10\%$ and C-index equal to 80%, we would need a minimum sample of 980 participants for a new model development for pre-eclampsia. Given that other outcomes are more prevalent than pre-eclampsia, they would require sample sizes smaller than the above figure.

f. Data collection

Following informed consent, participants' 12-week scans will be performed by the study sonographer. Once viability of the pregnancy and normal fetal anatomy is confirmed, the additional ultrasound adiposity measures needed for the study will be performed by the study sonographer. After ultrasound and any other clinical procedures are completed, the rest of the data collection will be performed by a female member of the research team, in a private room. Any women who do not consent to participating in the research will still have their 12-week scan carried out as planned, but no further measurements specific to the research will be taken.

Adiposity measures

The following ultrasound and anthropometry measurements will be taken.

Ultrasound scans:

- *Subcutaneous abdominal fat volume*
- *Visceral abdominal fat volume*
- *Total abdominal fat*

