Measurements of subcutaneous and visceral fat will be performed by trained operators (sonographer) using a GE E8 ultrasound machine with 2-5 MHz curvilinear probe. Methods described by Martin *et al.* (27) will be used to obtain the measurement. Ultrasound settings and patient position will be standardised to insure consistency of the procedure. Further, image capture will be standardised for breathing movements (on expiration) and bladder filling. Midline transverse section of the maternal abdomen will be obtained approximately 1 cm above the umbilicus to allow visualisation of transverse section of the abdominal aorta at the far field of the screen.

- Subcutaneous fat (SAT) measurement will be obtained from outer border of the subcutaneous fat layer to the outer border of rectus abdominus at the level of linea alba.
- Visceral fat (VAT) measurement will be obtained from the inner border of rectus abdominus at the level of linea alba to the anterior wall of the aorta.
- Total abdominal fat (TAT) will be calculated as a sum of SAT and VAT.

Three consecutive measurements will be performed and average of three will be employed in the predictive model. In a small sub-set of participants, measurement will be repeated by a second operator to assess inter-rater reliability of the ultrasound technique.

In addition to the above measurements of SAT and VAT, an alternative method of measuring these by ultrasound will be deployed to establish optimal methods for future implementation. SAT and VAT will be measured at the sagittal plane of xiphisternum as described by Cremona *et al* (28).

Anthropometry:

- Waist circumference, measured at the narrowest point of the abdomen between the lower costal (10th rib) border and the top of the iliac crest, perpendicular to the long axis of the trunk, at the end of normal expiration and with the abdominal muscles relaxed, to the nearest 0.1 centimetre.
- Hip circumference, measured at the greatest posterior protuberance of the buttocks, perpendicular to the long axis of the trunk, with the gluteal muscles relaxed and the feet together, over light clothing and to the nearest 0.1 centimetre.
- Height will be measured to the nearest 0.1 centimetre with shoes removed and the participant's head positioned in the Frankfort plane.
- Weight will be measured, in light clothing to the nearest 100g.

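### The check that 1400 women suffice counts 7 coefficients, but the planned models allow non-linear and multi-category terms, and the predictors called fixed are not fixed in the protocol

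*Protocol*

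**What the plan says.** Section 8e: "A sample of 1400 women will be recruited to the study". That number first came from a rule of ten events per variable. The section then reports a newer calculation as confirming it: "The sample size calculation is based on a maximum of 7 variables being included in the model". The outcome is pre-eclampsia, taken as the least common, with "estimated prevalence of approximately 5-6% of pregnancies in the UK". The targets are at most 10% shrinkage and a "C-index equal to 80" per cent, and the resulting minimum is 980.

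Section 8g describes the models that this number must support. Each outcome gets its own multiple logistic regression if no single adiposity measure beats BMI. There will not "be any variable selection since our predictors are already fixed". On functional form: "Nonlinear trend in continuous predictors will be explored using either fractional polynomials or restricted cubic splines". Internal validation uses 200 bootstrap samples to give an optimism-adjusted c-index and calibration slope.

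Three other places bear on whether the predictors are fixed:

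- Appendix 2 has 41 rows under its predictor heading: 12 body measures and 29 socio-demographic or clinical items.
- Section 8f adds 14 calculated indices, the skinfold sum and total abdominal fat (16 derived quantities), and allows further indices to be considered if they appear in the literature.
- Section 11 says that the variables that predict best will go forward to validation in a later study.

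**The concern.** The shrinkage criterion counts estimated coefficients. A continuous predictor with a curve, or a factor with several categories, uses more than one. If the sample size check counts variables while the analysis spends more coefficients than variables, the check covers a smaller model than the one planned, and overfitting may exceed the stated limit.

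The second part concerns the validation. A cap of seven and the absence of selection are compatible only if the seven are chosen without using the outcome data. The protocol says that the predictors are fixed but gives a much longer, open list. If outcome data were used to choose among predictors, adiposity measures or functional forms, a bootstrap that did not repeat the choice would leave the optimism-adjusted c-index and calibration slope too favourable. Those quantities answer the protocol's third objective.

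**Working it through.** **Inputs.** From section 8e: N = 1400; 7 variables; prevalence 5% to 6%; C-index 0.80; shrinkage of at most 10%, read as a uniform shrinkage factor S of at least 0.90; stated minimum 980. Two assumptions are mine: the linear predictor is normal with equal variance in cases and non-cases (needed to turn the C-index into an R²), and the number of terms per predictor, which the protocol does not give.

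**From C-index to R².** The mean difference in the standardised linear predictor is √2 × Φ⁻¹(0.80) = 1.190. With L1 and L0 the expected log-likelihood per woman under the model and under the prevalence alone, Cox-Snell R² = 1 − exp(−2(L1 − L0)). This gives 0.0623 at 5% and 0.0730 at 6%.

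**Reproducing 980.** With P parameters, n = P / ((S − 1) ln(1 − R²/S)).

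- At 5%: ln(1 − 0.0623/0.90) = −0.0717, so n = 7 / (0.1 × 0.0717) = 976. The stated 980 is within 0.5% of this.
- At 5.5% the result is 895, and at 6% it is 828, so the protocol's figure matches 5% prevalence and P = 7.
- The other usual criteria (optimism in R², overall risk, mean absolute prediction error) need at most 411 women at P = 7 and do not bind.
- The older rule also reproduces: 7 × 10 / 0.05 = 1400.

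**How many parameters 1400 supports.** Each parameter costs 976/7, about 139 women, at 5% and 828/7, about 118, at 6%. At S = 0.90, 1400 women therefore support 1400 × 0.1 × 0.0717 = 10.04, that is 10 parameters, at 5%. At 6%, ln(1 − 0.0730/0.90) = −0.0846, and the result is 11.85, that is 11 parameters.

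**Required n and expected S.** S at 1400 solves (1 − S) × (−ln(1 − R²/S)) = P/1400. Required n is rounded up.

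| Parameters | Example | n at 5% | S at 1400, 5% | n at 6% | S at 1400, 6% |
|---|---|---|---|---|---|
| 7 | one term each | 976 | 0.93 | 828 | 0.94 |
| 10 | three extra terms | 1,395 | 0.90 | 1,182 | 0.91 |
| 14 | two terms each (assumed) | 1,952 | 0.87 | 1,655 | 0.88 |
| 21 | three terms each (assumed) | 2,928 | 0.81 | 2,482 | 0.84 |

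The target is lost at 5% prevalence once four of the seven predictors carry one extra term each (7 + 4 = 11 parameters, 1,534 women). At 6% it is lost once five do (12 parameters, 1,418 women).

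**Fixed predictors.** Section 8e assumes at most seven. Appendix 2 offers 41 rows and section 8f a further 16 derived quantities with an open end, and no section says which seven apply to any outcome. Section 8g makes the multivariable step depend on how single measures perform against BMI, and section 11 carries forward the best performers. Both of these choices use the data.

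**The case against.** The strongest defence is that the stated arithmetic is right. Seven single-term predictors meet the target with room to spare (S about 0.93), and there is slack for three more parameters at 5% prevalence or four at 6%. Many listed candidates are yes/no history items that cost one coefficient each, and non-linearity is only to be explored. All of this stands. A reader might infer that the 10% target is missed; the documents do not show that, only that it is not assured.

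A reader might also infer a model with all 41 listed rows. The protocol does not plan one. Section 8e caps the model at seven, and Appendix 2 is a list of data items serving about 20 separately modelled outcomes, some rows being plainly outcome-specific. For the same reason the exact dependence in "Total abdominal fat (TAT) will be calculated as a sum of SAT and VAT" is not a defect: section 8g assesses adiposity measures one at a time, and nothing says that all three enter one model.

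Nor do the documents show a hidden selection step. Choosing seven predictors in advance from the literature is not data-driven and adds no optimism. Naming them, with knots and degrees of freedom, may properly be left to an analysis plan that is not shown. What remains is that the protocol itself asserts sufficiency from a count of variables, and itself says that the predictors are fixed while its other sections leave them open.

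Finally, the planned bootstrap would measure overfitting rather than hide it. That holds only if every data-driven step is repeated in each resample, which section 8g does not say.

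**Conclusion.** The concern holds in a limited form. The confirmation that 1400 is sufficient is valid for up to 10 parameters for pre-eclampsia at 5% prevalence, or 11 at 6%. It does not extend automatically to seven variables modelled as section 8g allows. With two terms for each of seven predictors, expected shrinkage at 1400 is about 13% (12% at 6%) against the target of 10%; with three terms each, it is about 19% (16%). These figures rest on the protocol's C-index of 0.80, the normal linear predictor used for the conversion, and the assumed number of terms.

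Separately, the sentence ruling out selection does not agree with the rest of the protocol. Whether any optimism goes uncorrected depends on how the predictors are eventually chosen, which the protocol does not settle.

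**What to change.** 1. In section 8e, state that 1400 supports at most 10 model parameters for pre-eclampsia at 5% prevalence (11 at 6%), counting non-linear terms and category indicators. Keep each model within that number, or use penalised estimation where it is exceeded.
2. In section 8g, replace the sentence on selection with wording such as: predictors are pre-specified for each outcome, at most seven, before outcome data are examined; any data-driven choice of predictor, adiposity measure or functional form is repeated within each bootstrap resample; final coefficients are shrunk by the optimism-adjusted calibration slope.

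This is a change of wording, with slightly more computing and no extra women. The price is a less comfortable margin: 1400 − 980 = 420 women for seven parameters becomes 1400 − 1,395 = 5 for ten at 5% prevalence. It should be settled before outcome data are examined, because pre-specification cannot be recovered afterwards.
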